#### 6.6.2 Secondary endpoints

#### FAAMS

See [Table 3.2.1](#) The Foot and Ankle Ability Measure (FAAM) is a self-report outcome instrument to assess physical function for individuals with foot and ankle related impairments. Like the EQ-5D, three language versions of the FAAM questionnaire were used. The FAAM consists of 29-item questions divided into two subscales: 21-item activities of daily living (ADL) subscale, 8-item sports subscale. Each item is scored on a 5-point Likert scale (4 to 0) from 'no difficulty at all' to 'unable to do'. Responses of "not applicable" are not counted. The score on each of the items are added together to get the subscale total score. The ADL subscale total score range from 0 to 84 and 0 to 32 for the sports subscale. The patient score for the ADL and sports subscale will be transformed to percentage scores by considering the highest possible score for non-missing items. Higher score indicates higher level of function for each subscale, with 100% representing no dysfunction (Martin et al., 2009).

See [Table 3.2.2](#) Patients assessed their current level of function as Normal, Nearly Normal, Abnormal, or Severely Abnormal. Summaries will be presented for each Wright device and visit.

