**5.4 Endpoints**

The primary endpoint is to demonstrate the safety and performance of the Wright product by:

- Comparing the improvements in patient-reported pain and social interaction for quality of life from pre-op through post-operatively, assessed by the EQ-5D-5L

Secondary endpoints:

- Comparing the improvement in patient-reported function scores from pre-op through post-operatively, assessed by the Foot and Ankle Ability Measure (FAAM)
- Identifying and reporting the safety of the implant in terms of complications and adverse events.
- Conducting a surgeon survey including radiographic assessment of fusion and consolidation time
- Conducting patient surveys to assess current implant status (to include complications)

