### 3. Statistical Procedure

#### 3.1. FRAMEWORK

The purpose of this statistical analysis plan is to guide the analysis and production of statistical output for the Wright Foot & Ankle Post-Market Observational Study. The company decided to discontinue enrollment to the study on November 1, 2021. At study end date, there were 122 patients enrolled in the study. The sample size of 40 patients per device that was originally planned in the study was therefore not met.

The study required at least 40 sample size for each Wright medical device (See INT19-MDR-001 Protocol, Version 3). For the same sample size parameters in the protocol  $n=10$ , will yield a power of 0.5. Thus, for the purpose of reporting statistically valid outcomes, descriptive summary statistics will be presented for Wright devices implanted in at least 10 patients enrolled in the study. Patient data on devices that has less than 10 implanted patients will be provided in the listings to be made available for future study or reference. Appendix Table 1 lists the Wright devices that are included in the study.

As the goal of the study is to determine the performance and safety of each device under investigation, analysis of outcomes will be done for each device the patient received. Note that a patient may have received more than one of the Wright devices. In all analysis of outcomes, patient level data will be included in the analysis for each device he/she received.

All analysis to be conducted are of descriptive nature only. No test of hypothesis will be performed. All quantitative variables, including those based on calculations (i.e., improvement from baseline), will be analyzed with a case summary evaluation before the detailed characteristics and parameter can be evaluated. A case summary contains a listing of the number of valid cases/values, missing cases/values (if any) and total cases/values in the specific analysis. The mean and median will be reported to assess the average or centrality of quantitative variables. Improvement from baseline in patient reported outcome (PROM) will be assessed at each post-surgery visit. Improvement will be based on the difference in raw scores.

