Whenever the available data allows, the standard deviation, interquartile range (IQR) and maximum and minimum will be calculated. All quantitative variables will be assessed for normality via the Shapiro-Wilk test. The 95% confidence interval (CI) of the mean will be presented when the normality of the data is met.

All qualitative variables, including those based on summaries (secondary elements), will be analyzed listing the proportions, frequencies, column and row totals and missing proportion (if any).

The proportion of device surviving at each visit will be summarized for each device. Rates will be computed based on available data. Missing data will not be imputed.

No imputations for missing data will be conducted.

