**Table 3.2.1 FAAM score by device and visit.**

Wright device	Baseline				Follow-up Visit				Final Visit			
	n	mean±sd	min,max	95% CI	n	mean±sd	min,max	95% CI	n	mean±sd	min,max	95% CI
Device 1												
FAAM SANE	xx	xx.x±xx.x	xx.x, xx.x	(xx.x, xx.x)	xx	xx.x±xx.x	xx.x, xx.x	(xx.x, xx.x)	xx	xx.x±xx.x	xx.x, xx.x	(xx.x, xx.x)
Sports Subscale	xx	xx.x±xx.x	xx.x, xx.x	(xx.x, xx.x)	xx	xx.x±xx.x	xx.x, xx.x	(xx.x, xx.x)	xx	xx.x±xx.x	xx.x, xx.x	(xx.x, xx.x)
ADL Subscale	xx	xx.x±xx.x	xx.x, xx.x	(xx.x, xx.x)	xx	xx.x±xx.x	xx.x, xx.x	(xx.x, xx.x)	xx	xx.x±xx.x	xx.x, xx.x	(xx.x, xx.x)
Change from Baseline												
FAAM SANE					xx	xx.x±xx.x	xx.x, xx.x	(xx.x, xx.x)	xx	xx.x±xx.x	xx.x, xx.x	(xx.x, xx.x)
Sports Subscale					xx	xx.x±xx.x	xx.x, xx.x	(xx.x, xx.x)	xx	xx.x±xx.x	xx.x, xx.x	(xx.x, xx.x)
ADL Subscale					xx	xx.x±xx.x	xx.x, xx.x	(xx.x, xx.x)	xx	xx.x±xx.x	xx.x, xx.x	(xx.x, xx.x)
Device 2												
FAAM SANE	xx	xx.x±xx.x	xx.x, xx.x	(xx.x, xx.x)	xx	xx.x±xx.x	xx.x, xx.x	(xx.x, xx.x)	xx	xx.x±xx.x	xx.x, xx.x	(xx.x, xx.x)
Sports Subscale	xx	xx.x±xx.x	xx.x, xx.x	(xx.x, xx.x)	xx	xx.x±xx.x	xx.x, xx.x	(xx.x, xx.x)	xx	xx.x±xx.x	xx.x, xx.x	(xx.x, xx.x)
ADL Subscale	xx	xx.x±xx.x	xx.x, xx.x	(xx.x, xx.x)	xx	xx.x±xx.x	xx.x, xx.x	(xx.x, xx.x)	xx	xx.x±xx.x	xx.x, xx.x	(xx.x, xx.x)
Change from Baseline												
FAAM SANE					xx	xx.x±xx.x	xx.x, xx.x	(xx.x, xx.x)	xx	xx.x±xx.x	xx.x, xx.x	(xx.x, xx.x)
Sports Subscale					xx	xx.x±xx.x	xx.x, xx.x	(xx.x, xx.x)	xx	xx.x±xx.x	xx.x, xx.x	(xx.x, xx.x)
ADL Subscale					xx	xx.x±xx.x	xx.x, xx.x	(xx.x, xx.x)	xx	xx.x±xx.x	xx.x, xx.x	(xx.x, xx.x)
:												
Device k												
FAAM SANE	xx	xx.x±xx.x	xx.x, xx.x	(xx.x, xx.x)	xx	xx.x±xx.x	xx.x, xx.x	(xx.x, xx.x)	xx	xx.x±xx.x	xx.x, xx.x	(xx.x, xx.x)
Sports Subscale	xx	xx.x±xx.x	xx.x, xx.x	(xx.x, xx.x)	xx	xx.x±xx.x	xx.x, xx.x	(xx.x, xx.x)	xx	xx.x±xx.x	xx.x, xx.x	(xx.x, xx.x)
ADL Subscale	xx	xx.x±xx.x	xx.x, xx.x	(xx.x, xx.x)	xx	xx.x±xx.x	xx.x, xx.x	(xx.x, xx.x)	xx	xx.x±xx.x	xx.x, xx.x	(xx.x, xx.x)
Change from Baseline												
FAAM SANE					xx	xx.x±xx.x	xx.x, xx.x	(xx.x, xx.x)	xx	xx.x±xx.x	xx.x, xx.x	(xx.x, xx.x)
Sports Subscale					xx	xx.x±xx.x	xx.x, xx.x	(xx.x, xx.x)	xx	xx.x±xx.x	xx.x, xx.x	(xx.x, xx.x)
ADL Subscale					xx	xx.x±xx.x	xx.x, xx.x	(xx.x, xx.x)	xx	xx.x±xx.x	xx.x, xx.x	(xx.x, xx.x)

Note:

ADL - activities of daily living

SANE - single assessment numeric evaluation

Tale 3.2.2 FAAM overall rating by device and visit

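### The four-category FAAM overall rating has no within-patient summary: Table 3.2.2 gives only separate baseline and final-visit percentages

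*SAP*

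**What the plan says.** Protocol 5.4 makes the gain in FAAM function scores from before to after surgery a secondary endpoint, and the schedule in Protocol 6.1.2 collects the FAAM pre-operatively, at the final clinical visit and, where needed, yearly.

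SAP 6.6.2 (FAAMS) describes the overall rating: "Patients assessed their current level of function as Normal, Nearly Normal, Abnormal, or Severely Abnormal". The only analysis instruction that follows is "Summaries will be presented for each Wright device and visit". The shell for Table 3.2.2, titled "FAAM overall rating by device and visit", has a Baseline block and a Final Visit block. Each cell carries its own numerator, denominator and percentage. It has no shift table, no count of patients improved or worsened, and no row limited to patients rated at both visits.

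The other before-and-after effectiveness tables differ. Table 3.2.1 has a block headed "Change from Baseline" for SANE, Sports and ADL, Table 3.1 has one for the EQ-5D, and Table 4.2 has an improvement block for the radiographic angles.

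SAP 5 defines a single Treated population. SAP 4.6 requires the number and percentage missing to be shown for each analysed variable at each post-operative assessment. SAP 3.1 rules out imputation.

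**The concern.** The question for this item is whether patients rate their function better after surgery than before. The planned table answers a different one: how the ratings were distributed among those who answered at each visit. A reader can only compare the two blocks, and that comparison has two weaknesses.

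- **Composition.** The final-visit block need not describe the same patients as the baseline block. If loss is related to the rating, the percentages move with no individual change. Such loss is plausible: Protocol 6.2.2 discontinues a subject whose study device is removed unless another study device remains, Table 1.1 lists adverse event and loss to follow-up as reasons for discontinuation, and Table 1.5 has a deviation type for questionnaires not completed.
- **Cancellation.** Even with no loss, equal numbers improving and worsening leave the percentages unchanged. The number who worsened matters in a study meant to show safety and performance, and the shell cannot supply it.

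**Working it through.** The plan gives no figure for this item. Its only sample-size calculation concerns EQ-5D precision: (1.96 × 0.313 / 0.1)² = 37.6, rounded up to the stated 38. That reproduces but does not bear on the rating. The documents give no drop-out rate and no baseline distribution of the rating, so every figure below rests on assumed inputs, apart from the minimum of 10 implanted patients for a device summary (SAP 3.1).

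**1. Composition, smallest device group.** Ten patients, 5 rated Normal or Nearly Normal at baseline, three lost, nobody changes category.

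| Who is lost | Baseline | Final visit | Apparent change | True change in the 7 paired patients |
|---|---|---|---|---|
| 3 poorly rated | 5/10 = 50.0% | 5/7 = 71.4% | +21.4 points | 0 |
| 3 well rated | 5/10 = 50.0% | 2/7 = 28.6% | −21.4 points | 0 |

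With one or two poorly rated patients lost, the final figures are 5/9 = 55.6% (+5.6) and 5/8 = 62.5% (+12.5). These are extreme cases, since all loss falls on one side.

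**2. Composition, partial dependence.** Let p be the baseline share rated Abnormal or worse, ra the proportion of these patients who return a final form, and rb the proportion among the others. With no one changing, the expected final-visit share is

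p·ra / (p·ra + (1 − p)·rb).

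| p | ra | rb | Final-visit share | Apparent gain |
|---|---|---|---|---|
| 0.5 | 0.6 | 0.8 | 0.30/0.70 = 42.9% | 7.1 points |
| 0.5 | 0.5 | 0.8 | 0.25/0.65 = 38.5% | 11.5 points |
| 0.5 | 0.5 | 0.9 | 0.25/0.70 = 35.7% | 14.3 points |
| 0.7 | 0.6 | 0.8 | 0.42/0.66 = 63.6% | 6.4 points |
| 0.7 | 0.5 | 0.8 | 0.35/0.59 = 59.3% | 10.7 points |
| 0.7 | 0.5 | 0.9 | 0.35/0.62 = 56.5% | 13.5 points |
| 0.5 | 0.8 | 0.5 | 0.40/0.65 = 61.5% | −11.5 points |
| any | equal | equal | p | 0 |

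Milder loss gives less. With p = 0.5 and poorly rated patients twice as likely to drop out, overall loss of 10%, 20% and 30% gives expected artefacts of 1.9, 4.2 and 7.1 points. The last is the 0.6 versus 0.8 row.

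**3. Cancellation.** Ten patients, none lost, 5 in the two better categories at baseline. Two move up into them and two move down out of them. Both blocks read 5/10 = 50.0%, although 2 of 10 patients (20%) fell from the better pair of categories to the worse pair.

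**4. What the existing safeguards recover.** Cell denominators and the SAP 4.6 missing counts would show 10 falling to 7 in step 1. They would not show whether the 7 changed, and they show nothing unusual in step 3.

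**The case against.** The strongest reply is that this is one supplementary categorical item in an instrument already analysed as change. SANE, ADL and Sports all have change from baseline in Table 3.2.1, the SAP is descriptive throughout, and the denominators and missing counts make loss visible. All of that is right, and it limits the importance of the point. It does not supply the missing result, because visible loss is not within-patient change.

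Four stronger readings are tempting, and the documents do not support them.

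- **A broken commitment.** A reader might infer that SAP 3.1 promises a change analysis here, since it states "Improvement from baseline in patient reported outcome (PROM) will be assessed at each post-surgery visit". The next sentence is "Improvement will be based on the difference in raw scores", and both stand in a paragraph on quantitative variables. Qualitative variables have their own rule of frequencies and proportions, which Table 3.2.2 follows. No score is assigned to the four categories.
- **An available-data rule for this rating.** The words "Rates will be computed based on available data. Missing data will not be imputed" follow directly on a sentence about device survival. For the rating, only the separate general statement against imputation applies.
- **Different patients in the two blocks.** With one Treated population, those rated at the final visit are largely a subset of those rated at baseline.
- **Drop-out by itself inflates the result.** It does so only if loss is related to the rating, and the sign reverses if better rated patients are the ones lost.

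It is also fair that a 16-cell shift table on about 10 patients would be mostly empty, and that an exact 95% interval at 5/10 runs from about 19% to 81%. The fix is scaled accordingly.

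**Conclusion.** The point holds as a modest gap in presentation. The FAAM overall rating is a before-and-after measurement with no planned within-patient summary, unlike the measures in Tables 3.1, 3.2.1 and 4.2. Comparing its two blocks can mislead if loss depends on the rating, and can hide patients who worsened even without loss.

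The size cannot be fixed from the documents. The calculations show apparent shifts from about 2 points to about 21 points in either direction, depending on assumed return rates and baseline distribution, and zero on average if loss is unrelated to the rating. The consequence is confined to one descriptive secondary summary and does not touch the primary EQ-5D analysis or the numeric FAAM results.

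**What to change.** In Table 3.2.2, keep the existing margins and add for each device summarised:

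- the number and percentage of patients improved, unchanged and worsened by category, among those with both ratings;
- the baseline distribution for those paired patients, next to the one for all patients rated at baseline;
- the number excluded for want of a second rating.

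Give a full baseline-by-final shift table where numbers allow. An exact 95% confidence interval for the proportion improved is optional and will be wide in the smallest groups.

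The paired summary removes the composition artefact but cannot show what happened to patients who were lost. This is why the number excluded and the two baseline rows belong beside it.

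The cost is one revised table shell, a sentence in SAP 6.6.2 and a little programming on data already collected. No hypothesis test is added, so the descriptive framework of SAP 3.1 is unchanged.

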## SURGEON ASSESSMENT AND RADIOGRAPHIC OUTCOME

See [Table 4.1](#). At the final visit of the patient, the attending surgeon assessed the surgical foot to assess the outcome. The surgeon also assessed the radiographic outcome of the surgery. For each Wright device of interest, the following will be summarized:

- Days from surgery to radiographic evaluation
- Imaging procedure done: standing AP/lateral, hindfoot alignment view, CT, MRI, Other
- Surgeon opinion on Wright product performance
- Bony union outcome for joint arthrodesis device

See [Table 4.2](#). The surgeon assessment of angle deformity correction based on radiograph will be summarized for the following:

- Angle deformity correction for hallux valgus deformity: Halux Valgus angle, Intermetatarsal angle, Distal Metatarsal Articular Angle
- Angle deformity correction for flatfoot or charcot: Mearys angle, Talonavicular Angle, Other
- Surgeon observed adverse event (Y/N)

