**Table 4.2 Surgeon assessment of deformity correction based on radiograph by device.**

Wright device	Baseline							Final visit							Improvement						
	n	mean	sd	min	max	95% CI	n	mean	sd	min	max	95% CI	n	mean	sd	min	max	95% CI			
Device 1																					
Degree of deformity correction																					
Hallux valgus procedure																					
Hallux valgus	xx.x	xx.x	xx.x	xx.x	xx.x	(xx.x, xx.x)	xx.x	xx.x	xx.x	xx.x	xx.x	(xx.x, xx.x)	xx.x	xx.x	xx.x	xx.x	xx.x	(xx.x, xx.x)			
Intermetatarsal Angle	xx.x	xx.x	xx.x	xx.x	xx.x	(xx.x, xx.x)	xx.x	xx.x	xx.x	xx.x	xx.x	(xx.x, xx.x)	xx.x	xx.x	xx.x	xx.x	xx.x	(xx.x, xx.x)			
DMA Angle	xx.x	xx.x	xx.x	xx.x	xx.x	(xx.x, xx.x)	xx.x	xx.x	xx.x	xx.x	xx.x	(xx.x, xx.x)	xx.x	xx.x	xx.x	xx.x	xx.x	(xx.x, xx.x)			
Flatfoot or charcot procedure																					
Mearys Angle	xx.x	xx.x	xx.x	xx.x	xx.x	(xx.x, xx.x)	xx.x	xx.x	xx.x	xx.x	xx.x	(xx.x, xx.x)	xx.x	xx.x	xx.x	xx.x	xx.x	(xx.x, xx.x)			
TNV Angle	xx.x	xx.x	xx.x	xx.x	xx.x	(xx.x, xx.x)	xx.x	xx.x	xx.x	xx.x	xx.x	(xx.x, xx.x)	xx.x	xx.x	xx.x	xx.x	xx.x	(xx.x, xx.x)			
Other	xx.x	xx.x	xx.x	xx.x	xx.x	(xx.x, xx.x)	xx.x	xx.x	xx.x	xx.x	xx.x	(xx.x, xx.x)	xx.x	xx.x	xx.x	xx.x	xx.x	(xx.x, xx.x)			
Device 2																					
Degree of deformity correction																					
Hallux valgus procedure																					
Hallux valgus	xx.x	xx.x	xx.x	xx.x	xx.x	(xx.x, xx.x)	xx.x	xx.x	xx.x	xx.x	xx.x	(xx.x, xx.x)	xx.x	xx.x	xx.x	xx.x	xx.x	(xx.x, xx.x)			
Intermetatarsal Angle	xx.x	xx.x	xx.x	xx.x	xx.x	(xx.x, xx.x)	xx.x	xx.x	xx.x	xx.x	xx.x	(xx.x, xx.x)	xx.x	xx.x	xx.x	xx.x	xx.x	(xx.x, xx.x)			
DMA Angle	xx.x	xx.x	xx.x	xx.x	xx.x	(xx.x, xx.x)	xx.x	xx.x	xx.x	xx.x	xx.x	(xx.x, xx.x)	xx.x	xx.x	xx.x	xx.x	xx.x	(xx.x, xx.x)			
Flatfoot or charcot procedure																					
Mearys Angle	xx.x	xx.x	xx.x	xx.x	xx.x	(xx.x, xx.x)	xx.x	xx.x	xx.x	xx.x	xx.x	(xx.x, xx.x)	xx.x	xx.x	xx.x	xx.x	xx.x	(xx.x, xx.x)			
TNV Angle	xx.x	xx.x	xx.x	xx.x	xx.x	(xx.x, xx.x)	xx.x	xx.x	xx.x	xx.x	xx.x	(xx.x, xx.x)	xx.x	xx.x	xx.x	xx.x	xx.x	(xx.x, xx.x)			
Other	xx.x	xx.x	xx.x	xx.x	xx.x	(xx.x, xx.x)	xx.x	xx.x	xx.x	xx.x	xx.x	(xx.x, xx.x)	xx.x	xx.x	xx.x	xx.x	xx.x	(xx.x, xx.x)			
:																					
Device k																					
Degree of deformity correction																					
Hallux valgus procedure																					

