**C. LISTING OF LISTINGS**

- Listing 1 Demographic Information
- Listing 2 Inclusion/Exclusion Criteria
- Listing 3 Protocol Deviations
- Listing 4 Medical History
- Listing 5 Surgical and Operative Information
- Listing 6 EQ-5D Score
- Listing 7 FAAMS Score
- Listing 8 Surgeon assessment and radiographic deformity correction assessment
- Listing 9 Adverse Events
- Listing 10 Study Completion

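### Table 4.2 gives the undefined flatfoot/Charcot category *Other* one pooled summary per device, which cannot be read as correction if it holds more than one type of angle

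*SAP*

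**What the plan says.** The SAP section on surgeon assessment and radiographic outcome sends angle measurements to Table 4.2 in two groups. The first is closed, with three named angles: "Angle deformity correction for hallux valgus deformity: Halux Valgus angle, Intermetatarsal angle, Distal Metatarsal Articular Angle". The second has two named angles and a residual category: "Angle deformity correction for flatfoot or charcot: Mearys angle, Talonavicular Angle, Other".

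The template in SAP Appendix 2 B, "Table 4.2 Surgeon assessment of deformity correction based on radiograph by device", has a block headed "Flatfoot or charcot procedure". In it *Other* has one numeric row for each placeholder device. The columns are n, mean, SD, minimum, maximum and 95% CI, each for baseline, final visit and improvement. Meary's angle and the talonavicular angle have the same columns. The opening of SAP section 6 says that the templates are to guide the programming and the report.

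SAP section 3.1 adds two limits. On which devices are summarised: "descriptive summary statistics will be presented for Wright devices implanted in at least 10 patients enrolled in the study". On the interval: "The 95% confidence interval (CI) of the mean will be presented when the normality of the data is met". Patient-level data are planned in "Listing 8 Surgeon assessment and radiographic deformity correction assessment".

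**The concern.** A residual category is, by its label, whatever is not one of the named angles. If two patients with the same device had different angles recorded there, the template would average measurements that need not share a normal range or a direction of correction. The resulting mean would move with the proportion of each angle in the sample, even if the correction in each angle stayed the same.

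SAP section 2.1 says that the study is to show performance partly through radiographic assessment, and that the results go to regulators and notified bodies. A per-device improvement figure, possibly with an interval, could be taken there as evidence of correction or of its absence.

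**Working it through.** **No figure to reproduce.** Table 4.2 is an empty template, so the check is of the text, followed by an illustration.

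**Text check.**

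1. Is *Other* defined, or limited to one angle? No, in neither document.
2. Is it split by angle name? No. The template has one row per device.
3. Is the direction of improvement fixed for angles? No. SAP 3.1 bases improvement on the difference in raw scores, but that sentence follows one about patient-reported outcomes. The SAP section on radiographic outcome and Table 4.2 give no sign rule.
4. Does SAP 4.8 help? It refers to the analysis chapter for details of calculated variables, and that chapter gives only the one-word label.
5. Is Listing 8 required to show the name of the angle? Its title does not say so.
6. Is the fault wider than one row? No. The hallux valgus block has no *Other* row.

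**Illustration (all inputs assumed).** Take 10 patients with one device and two angle types, A and B, with $n_A$ and $n_B$ patients, mean changes $d_A$ and $d_B$ in degrees, and a within-angle SD of change of 3 degrees. With $N = n_A + n_B$:

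- pooled mean: $m = (n_A d_A + n_B d_B)/N$
- pooled SD: $s = \sqrt{[(n_A-1)3^2 + (n_B-1)3^2 + n_A(d_A-m)^2 + n_B(d_B-m)^2]/(N-1)}$
- 95% CI: $m \pm t_{0.975,\,N-1}\, s/\sqrt{N}$, with $t_{0.975,9} = 2.262$

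Worked case, changes of -10 and -4, five patients each: $m = (5(-10) + 5(-4))/10 = -7.0$. The sum of squares is $36 + 36 + 45 + 45 = 162$, so $s = \sqrt{162/9} = 4.24$. The half-width is $2.262 \times 4.24/\sqrt{10} = 3.04$, which gives -10.0 to -4.0.

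| Change A, B | Split | Mean | SD | 95% CI |
|---|---|---|---|---|
| -10, -10 (one type) | 5:5 | -10.0 | 2.8 | -12.0 to -8.0 |
| -10, -4 | 5:5 | -7.0 | 4.2 | -10.0 to -4.0 |
| -10, -4 | 8:2 | -8.8 | 3.8 | -11.5 to -6.1 |
| -10, +10 | 5:5 | 0.0 | 10.9 | -7.8 to 7.8 |
| -10, +10 | 8:2 | -6.0 | 8.9 | -12.4 to 0.4 |

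The first row can be interpreted. In the others the mean shifts with the split although the change in each angle is fixed. The -10 and -4 rows show that opposite directions are not needed.

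**Does the normality rule catch this?** I simulated 50:50 mixes with the same within-angle SD of 3 and a Shapiro-Wilk level of 0.05, also assumed because the SAP states none. At 10 patients, normality is rejected in about 96% of samples for -15/+15, about 59% for -10/+10 and about 3% for -10/-4. At 20 patients, it is rejected in about 98% of samples for -10/+10. The rule therefore often removes the CI for strongly opposed mixes and almost never for the milder one. The mean, SD, minimum and maximum are printed in every case.

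**The case against.** The strongest reply is that mixing is inferred from a label. The case report form is not among the documents, and nothing in them says that *Other* is a free-text field or that it differs between patients. This stands, so the point has to be conditional. A reader might infer that the row is bound to be meaningless. The documents do not support that, because a device whose *Other* entries are all one angle would give an interpretable mean, although an unlabelled one.

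A reader might also infer that a mean with a CI will be printed for every device. That is not so: SAP 3.1 limits summaries to devices with at least 10 implanted patients and shows the CI only when normality is met. Both limits are partial. The first counts implanted patients and not patients with an *Other* angle, so the row could rest on very few values. The second tests the shape of the distribution and not whether the values measure the same thing.

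Third, a reader might infer that opposite corrections will cancel to no improvement. This depends on a sign convention that the SAP leaves open for angles. If improvement were scored towards correction, changes of -10 and +10 would both count as +10. The printed SD, minimum and maximum would also warn of a wide spread. Cancellation is possible but not established. Scoring towards correction would not remove the mixing problem, because angles corrected by 10 and by 4 degrees would still average to 7.

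Finally, the template is generic and Listing 8 already carries patient values. That makes the fix cheap, but it does not tell the programmer to leave the *Other* row empty.

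**Conclusion.** The point holds in conditional form. For each device with at least 10 implanted patients, the flatfoot/Charcot block of Table 4.2 calls for one pooled mean, SD, minimum and maximum for an undefined category and, where normality is met, a 95% CI. If *Other* holds more than one type of angle, the figure depends on the mix of angles and cannot be interpreted as correction. If it holds one type, the reader still cannot tell which angle was corrected.

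No numerical size can be taken from the documents; the values in the illustration are assumed and show only the mechanism. The impact is small. SAP 3.1.3 lists deformity correction among the additional analyses, protocol section 5.4 does not name angles among its endpoints, and SAP 3.1 states that "All analysis to be conducted are of descriptive nature only". The primary endpoint, EQ-5D-5L, is unaffected.

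**What to change.** In the SAP section on surgeon assessment and radiographic outcome, and in Table 4.2:

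- Replace the pooled *Other* statistics with a count of patients who have an *Other* angle, by device.
- Summarise such an angle only under its own name, and only where at least a pre-stated minimum number of patients with that device share it. Write the minimum into the SAP before the data are reviewed, so that it is not chosen afterwards.
- Show all other values in Listing 8, with the name of the angle where it was recorded. Where it was not recorded, list the values without averaging them.

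The cost is a change to one row per device and one column in an existing listing. The downside is that a few sparse values are listed and not averaged.
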